- **MILD:** Awareness of signs or symptoms, but does not interfere with the patient's usual activity, or is a transient event that resolves without treatment and with no sequelae.
- **MODERATE:** A sign or symptom, which interferes with the patient's usual activity.
- **SEVERE:** Incapacity with inability to do work or usual activities.

Relationship of Adverse Events

It is the Investigator's responsibility to assess the relationship between all AEs and the study procedure.

The following guidelines should be used in determining the relationship of an AE to a device, study procedure, or other causality:

Not related	Temporal sequence between device usage and the event is such that the relationship is unlikely.
Unlikely related	Temporal sequence between device usage and the event is such that the relationship is not unlikely or the subject's condition or concomitant therapy could have caused the AE.
Possibly related	Temporal sequence is relevant or the event abates upon device usage completion or the event cannot be reasonably explained by the patient's condition.
Probably related	Temporal sequence is relevant and the event abates upon product device usage or reappearance of the event on repeat device usage (re-challenge).
Causal relationship	Temporal sequence between device usage and the event is such that the relationship is unlikely.

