12.2 Reporting Adverse Events

The Investigator is required to report all AEs experienced by the patient from the start of the ablation procedure (Visit 2A) until the patient completes Visit 5 (1 year after the first ablation procedure) or withdraws early (prior to Visit 5) to the Sponsor within 14 days of become aware of the AEs. All AEs (both serious and non-serious) must be reported in the AE eCRF. The Investigator will evaluate the severity of the event and its relatedness to the study device or procedure.

Any necessary medical management of the event will be recorded in the patient's medical record/source document. All AEs must be followed until resolution or until they become stable.

The Investigator will record all AEs (both serious and non-serious) in the source documents. CTC (Common Terminology Criteria) should be used when recording AEs. In addition, the following information should be recorded:

- Onset date
- Resolution date or date of death
- Severity of the event using CTCAE
- Action taken
- Event status (ongoing at study end or resolved)
- Relationship of AE to the ablation device used in the study
- Relationship of AE to the study procedure
- Indication of seriousness.

Data related to SAEs will be collected until event resolution, or until the event is considered stable, or until all attempts to determine the resolution of the event are exhausted. All AEs that are unresolved at study completion (or early termination) will be recorded as ongoing at study end.

Reporting Serious and Non-Serious Adverse Events to the Sponsor

The study site must report all SAEs, whether they are related to the device or procedure, to the Sponsor as soon as possible, but no later 72 hours of becoming aware of the SAE. The study site will report the SAE by entering the event into the EDC system via the Adverse Event eCRF, which will trigger an automated email to the Sponsor. Additional information, including the Investigator's assessment, may be added to the eCRF later; however, the study site must complete the AE eCRF within 72 hours of becoming aware of the SAE. If the Sponsor requires supporting documentation or other information, the Sponsor will contact the study site.

In the event of death, the Investigator must report all available information to the Sponsor.

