9.6 Safety Analyses

Safety will be assessed through the incidence of AEs and SAEs, which will be coded using MedDRA. The number and percentage of subjects reporting AEs and SAEs will be summarized at the MedDRA system organ class and preferred term level. Similar summaries will also be provided for AEs and SAEs related to the study device, as well as for AEs and SAEs related to the study procedure. Related events are those where the relationship is indicated as Unlikely, Possibly, Probably, or Causal. Summaries of all AEs and SAEs reported within the first 30 days after the initial ablation procedure will be generated. All reported adverse events will be listed.

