System Organ Class 4	Preferred Term 1	xx (xx.x%)
	Preferred Term 2	xx (xx.x%)

The following tables will have the same format as Table 14:

Table 15	Serious Adverse Events by System Organ Class and Preferred Term Full Analysis Set
Table 16	Adverse Events Related to the Study Device by System Organ Class and Preferred Term Full Analysis Set
Table 17	Serious Adverse Events Related to the Study Device by System Organ Class and Preferred Term Full Analysis Set
Table 18	Adverse Events Related to the Study Procedure by System Organ Class and Preferred Term Full Analysis Set
Table 19	Serious Adverse Events Related to the Study Procedure by System Organ Class and Preferred Term Full Analysis Set
Table 20	Adverse Events Related to the Study Device Within 30 Days of the Initial Ablation Procedure by System Organ Class and Preferred Term Full Analysis Set
Table 21	Serious Adverse Events Related to the Study Device Within 30 Days of the Initial Ablation Procedure by System Organ Class and Preferred Term Full Analysis Set

Table 22
 Target Lesion Details – Independent Reviewer
 Full Analysis Set

Characteristics	Overall (N = ##)
Lesion Location	
RUL	xx (xx.x%)
RML	xx (xx.x%)
RLL	xx (xx.x%)
LUL	xx (xx.x%)
LLL	xx (xx.x%)
Other	xx (xx.x%)
Distance from Pleura (cm)	
n	xx
Mean	xx.x
Standard Deviation	x.xxx
Median	xx.x
Minimum, Maximum	xx.x, xx.x
Largest Diameter (cm)	
n	xx
Mean	xx.x
Standard Deviation	x.xxx
Median	xx.x
Minimum, Maximum	xx.x, xx.x
Smallest Diameter (cm)	
n	xx
Mean	xx.x
Standard Deviation	x.xxx
Median	xx.x
Minimum, Maximum	xx.x, xx.x
Ablation Margin, Smallest Diameter (cm)	
n	xx
Mean	xx.x
Standard Deviation	x.xxx
Median	xx.x
Minimum, Maximum	xx.x, xx.x

Table 22
Target Lesion Details – Independent Reviewer
Full Analysis Set

Characteristics	Overall (N = ##)
Technical Success – Visit 2A/Day 0	
Yes	xx (xx.x%)
95% Exact Confidence Interval	xx.x%, xx.x%
Technique Efficacy at Day 30	
Yes	xx (xx.x%)
95% Exact Confidence Interval	xx.x%, xx.x%
Target Lesion Recurrence Day 30 to Month 12	
Yes	xx (xx.x%)
95% Exact Confidence Interval	xx.x%, xx.x%

The following listings will be generated for this study:

Listing 1	Inclusion/Exclusion Criteria All Subjects
Listing 2	Inclusion/Exclusion Criteria – Ablation Visit All Subjects
Listing 3	Study Visits All Subjects
Listing 4	Study Visit Details All Subjects
Listing 5	Demographics All Subjects
Listing 6	Pregnancy Test All Subjects
Listing 7	Medical History All Subjects
Listing 8	Surgical History All Subjects

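### Protocol 12.1 defines 'Causal relationship' with the same sentence as 'Not related', so an event with implausible timing could be graded into the related-event tables (minor)

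*Protocol*

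**What the plan says.** Protocol 12.1 sets out a five-level scale for the relationship of an adverse event: Not related, Unlikely related, Possibly related, Probably related, Causal relationship. Its lead-in makes the scale operative for device and procedure alike: "The following guidelines should be used in determining the relationship of an AE to a device, study procedure, or other causality". The definition of 'Not related' is "Temporal sequence between device usage and the event is such that the relationship is unlikely", and the definition of 'Causal relationship' is that same sentence.

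Protocol 12.2 makes relationship a recorded item, once for the device ("Relationship of AE to the ablation device used in the study") and once for the study procedure.

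SAP 9.6 then divides the recorded labels: "Related events are those where the relationship is indicated as Unlikely, Possibly, Probably, or Causal". By omission, only 'Not related' falls outside. The division feeds the related-event tables in the SAP Appendix, from Table 16 ("Adverse Events Related to the Study Device by System Organ Class and Preferred Term") through Table 19 ("Serious Adverse Events Related to the Study Procedure by System Organ Class and Preferred Term"). The shells of Tables 20 and 21 are also titled as device-related, for the first 30 days. The text of SAP 9.6, however, describes the 30-day summaries as covering all AEs and SAEs.

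**The concern.** A written definition is there so that investigators at different sites (4 to 8 were planned, Protocol 3.0) grade alike. Here the definition of the top category contradicts its own label and repeats the bottom category. A grader who follows the text for an event with implausible timing finds two rows that fit equally well. One keeps the event out of the related-event tables and the other puts it in.

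Device-related and procedure-related events are part of the first secondary objective (Protocol 5.2, SAP 1.1), in what the protocol's introduction calls the first experience with this system in transbronchial ablation. A reader who looks up what a 'Causal' grade means, whether in a table or in the adverse event listing, would also find a definition that says the opposite.

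There is a lesser fault in the next row. The timing clause of 'Unlikely related' says that "the relationship is not unlikely or the subject's condition or concomitant therapy could have caused the AE". The first part contradicts the label; the second part, an alternative explanation for the event, is sound.

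**Working it through.** No figure in the plan has to be reproduced. The check sets the passages side by side and traces events through them.

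**1. The two rows.** The 'Not related' and 'Causal relationship' definitions were compared word by word: 15 words each, identical.

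**2. The five rows against the SAP 9.6 rule.**

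| Label | Written definition | Side under SAP 9.6 |
|---|---|---|
| Not related | "Temporal sequence between device usage and the event is such that the relationship is unlikely" | Not related (by omission) |
| Unlikely related | timing makes the link 'not unlikely', or another cause is available | Related |
| Possibly related | "Temporal sequence is relevant or the event abates upon device usage completion or the event cannot be reasonably explained by the patient's condition" | Related |
| Probably related | relevant timing with abatement, or recurrence on repeat use | Related |
| Causal relationship | "Temporal sequence between device usage and the event is such that the relationship is unlikely" | Related |

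No label appears on both sides. One definition does.

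**3. Tracing three kinds of event through the literal text.**
- *Implausible timing.* It fits the first and last rows. Graded by the first it is left out; graded by the last it is counted as related. This is the only route to error through the duplicated row, and it runs upward.
- *Truly caused by the device or procedure.* It does not meet the written 'Causal' definition, but it meets 'Possibly' or 'Probably', both of which are counted. No such event is lost because of the duplicated row.
- *Plausible timing, graded 'Unlikely' through the faulty clause.* 'Unlikely' is already counted as related. Moving the grade up to 'Possibly' or 'Probably' changes no table.

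**4. Which tables use the split.** The adverse event shells are Tables 14 to 21: 21 − 14 + 1 = 8 tables.
- Tables 14-15 (all AEs, all SAEs): do not use it.
- Tables 16-19 (device and procedure, AEs and SAEs): use it, 4 tables.
- Tables 20-21 (first 30 days): use it as titled, but would not if built as the SAP 9.6 text describes them.

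So the split reaches 4 of 8 tables on the SAP text and 4 + 2 = 6 of 8 on the shell titles.

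**5. Scale.** Ten subjects were ablated (SAP section 7). One subject counted wrongly as related moves a table percentage by 1/10 = 10.0 points, for example from 0/10 = 0.0% to 1/10 = 10.0%. The documents hold no event-level data. The number of events wrongly counted through the duplicated row is therefore known only to lie between 0 and the number graded 'Causal'.

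**The case against.** The strongest reply is that the tables are built from the label ticked on the eCRF, not from the definition text. 'Causal relationship' is plain language, and an investigator would have to ignore its meaning to choose it for an event with implausible timing. The sponsor reviews all reported AEs and SAEs (Protocol 12.1), Tables 14-15 are untouched, and every adverse event is listed, so in 10 subjects each grade can be inspected. The eCRF wording is not in the documents, and sites may never have worked from this text. The table was also machine-read from PDF.

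Most of this stands, and it is why the point is minor. It does not remove the point. The protocol tells investigators to use these definitions, and one of them is wrong as written. An extraction fault is unlikely, because the sentence is complete, sits in its own labelled row, and is separated from its twin by three different rows.

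A reader might infer more, and the documents do not support it:
- *That the SAP rule is incoherent.* It assigns each label to one side and is sound on the labels.
- *That device-caused events could be hidden.* They still enter through 'Possibly' or 'Probably'.
- *That the related-event tables are wrong.* No misgraded event is shown.
- *That the assessment of the death that halted enrollment was affected.* Nothing says that it used this scale.

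**Conclusion.** The concern holds as a minor drafting error in an operative definition. The wording is certain on the text available; any effect on the tables is possible but not shown. If there is an effect, it is upward only, and it is confined to Tables 16-19, with Tables 20-21 added if the shell titles govern. It would be tempting to say flatly that six tables depend on the split, but SAP 9.6 and the shells of Tables 20-21 do not agree on this.

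The 'not unlikely' clause is a second, lesser slip that moves no event across the split.

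The conclusion assumes that the protocol's definitions, or a copy of them, were what the sites had in front of them. If the eCRF carried correct definitions, only the protocol text is at fault.

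**What to change.** 1. Correct the 'Causal relationship' row so that it differs from 'Not related' and sits at the top of the scale. Correct the timing clause of 'Unlikely related' so that it agrees with its label.
2. Before database lock, confirm and document which definitions the eCRF and the sites used. If they were correct, a note to file is enough.
3. Only if the faulty text was used, query the device and procedure relationship of events graded 'Causal' in the 10 subjects, and keep the original grades in the audit trail. Do not query 'Unlikely' grades: the fields listed in Protocol 12.2 do not record which clause was relied on, and upward re-grading would change no table.
4. If the database is already locked, state in the clinical study report which definitions were applied.

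The cost is a clarification note and one check of the eCRF text, with at most a small round of queries. The documents do not show that events are still being graded, so the benefit may lie only in how recorded grades are read. The downside is that any re-grading would be open-label and made after a known death, so it carries some hindsight. That is the reason to keep the original grades visible.

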12.2 Reporting Adverse Events

The Investigator is required to report all AEs experienced by the patient from the start of the ablation procedure (Visit 2A) until the patient completes Visit 5 (1 year after the first ablation procedure) or withdraws early (prior to Visit 5) to the Sponsor within 14 days of become aware of the AEs. All AEs (both serious and non-serious) must be reported in the AE eCRF. The Investigator will evaluate the severity of the event and its relatedness to the study device or procedure.

Any necessary medical management of the event will be recorded in the patient's medical record/source document. All AEs must be followed until resolution or until they become stable.

The Investigator will record all AEs (both serious and non-serious) in the source documents. CTC (Common Terminology Criteria) should be used when recording AEs. In addition, the following information should be recorded:

- Onset date
- Resolution date or date of death
- Severity of the event using CTCAE
- Action taken
- Event status (ongoing at study end or resolved)
- Relationship of AE to the ablation device used in the study
- Relationship of AE to the study procedure
- Indication of seriousness.

Data related to SAEs will be collected until event resolution, or until the event is considered stable, or until all attempts to determine the resolution of the event are exhausted. All AEs that are unresolved at study completion (or early termination) will be recorded as ongoing at study end.

Reporting Serious and Non-Serious Adverse Events to the Sponsor

The study site must report all SAEs, whether they are related to the device or procedure, to the Sponsor as soon as possible, but no later 72 hours of becoming aware of the SAE. The study site will report the SAE by entering the event into the EDC system via the Adverse Event eCRF, which will trigger an automated email to the Sponsor. Additional information, including the Investigator's assessment, may be added to the eCRF later; however, the study site must complete the AE eCRF within 72 hours of becoming aware of the SAE. If the Sponsor requires supporting documentation or other information, the Sponsor will contact the study site.

In the event of death, the Investigator must report all available information to the Sponsor.

The report of an SAE by a site does not constitute an admission that study personnel or the user facility (hospital/clinic) caused or contributed to the event. The study site is responsible for submitting AEs to the reviewing IRB/EC, per their IRB/EC procedures.

Regarding non-serious AEs, the study site is expected to complete the Adverse Event eCRF within 14 days of becoming aware of the event. The Investigator must assess expectedness, which also will be recorded in the AE eCRF. Supporting documentation may be requested, as needed.

13.0 PRODUCT COMPLAINTS

13.1 Product Complaint Definition

A product complaint is defined as any written, electronic, or oral communication that alleges deficiencies related to the identity, labeling, quality, durability, reliability, safety, effectiveness, or performance of a device after it is released for distribution (21CFR 820.3 (b)). A product complaint may or may not be associated with an AE/SAE.

Product complaints may include, but are not limited to:

1. Product contamination.
2. Defective components.
3. Device malfunction (the failure of a device to perform as intended for this study).

13.2 Reporting Product Complaints

All product complaints related to devices in the procedure shall be documented throughout the clinical investigation.

The study site must report product complaints related to a device manufactured by NeuWave Medical, Inc., in a timely manner, but no later than 24 hours of becoming aware of the event.

When any representative of the Sponsor becomes aware of a product complaint, the Sponsor representative must notify the Sponsor's Product Complaint Team within 24 hours of becoming aware of the event.

The Product Complaint Form must be emailed to the Sponsor Customer Complaint team

[REDACTED]

[REDACTED]

[REDACTED]

One copy of the processed form should be kept on-site and the device should be retained. Sponsor representatives will organize collection of the device for evaluation, as needed.

14.0 PUBLICATION PLAN

[figure not shown]
Publication and authorship policies should be determined and aligned with the clinical study agreement executed between operating company and each clinical site. Publication of the results of this study will be governed by J&J publication policies, including current and applicable Medical Device Publication Policy. Any presentation, abstract, or manuscript will be made available for review by the Sponsor prior to submission. Licensing agreements or copyrights applying to tools, work products or intellectual property used during the study should be observed and clearly displayed on study documentation and publications, wherever appropriate.

All manuscripts of data obtained from this clinical study will be reviewed and approved by the Sponsor, and each author, prior to any submission. Current and applicable Medical Device Publication Policy will be followed. The Sponsor will require a written agreement for any external author(s) prior to initiating any publication. All authors must disclose financial or personal affiliations that could be considered a conflict of interest.

15.0 APPENDICES

APPENDIX 1: Numeric Pain Rating Scale

The Numeric Pain Rating Scale (NPRS) can be administered verbally (therefore also by telephone) or graphically for self-completion. As mentioned above, the respondent is asked to indicate the numeric value on the segmented scale that best describes their pain intensity.

The original study protocol planned to continue study enrollment until 40 subjects were ablated (approximately 20 subjects ablated by interventional pulmonologists and 20 subjects ablated by thoracic surgeons) and completed Visit 3 (30 days \pm 7 days after the first ablation procedure). However, study enrollment was temporarily halted after 10 subjects were enrolled to convene a meeting of the Data Safety Monitoring Board (DSMB) following the death of one subject. While the DSMB recommended that the study could continue enrollment, the decision was made to permanently stop study enrollment and follow the 10 previously-enrolled subjects through the end of the study follow-up period of 1 year post-ablation. As such, this decision impacts several of the analyses originally planned in the study protocol and those changes will be identified in the appropriate sections throughout this SAP.

1 Study Overview

1.1 Study Objectives

The primary objective of the study was to evaluate the NeuWave Flex Microwave Ablation System in transbronchial ablation procedures for adult subjects with a medically inoperable primary soft tissue lesion, based on the following assessments:

- a. Device user experience survey
- b. Technical success
- c. Technique efficacy

Device user experience was collected from the treating physician who completed the User Experience Survey following each ablation procedure throughout the study, when applicable. The survey focused on procedure workflow and the user's assessment on ease/difficulty of using the device. The device user experience was designed to augment the Product Development Specialist's understanding of the usability of the Flex system and determine which enhancements, if any, are needed.

The secondary objectives were the following:

1. To evaluate safety through the monitoring of device-related and procedure-related adverse events (AEs) and all serious adverse events (SAEs), from start of ablation through 1-year post-ablation.
2. To establish device and procedure effectiveness by following subjects for 1-year post-ablation to ensure completeness and durability of treatment effect, based on standard endpoints in microwave ablation, as follows:
 - a. Primary efficacy rate
 - b. Secondary efficacy rate
 - c. Local soft lesion recurrence

- d. Length of hospital stay, measured from post-ablation to discharge
 - e. Hospital readmission rate.
3. To calculate hospital readmission rate, defined as any readmission to the hospital within 30 days of the first ablation procedure (Visit 2A).

The exploratory objectives were the following:

- 1. To assess the quality of life post microwave ablation of the lung throughout the 1 year \pm 1 month follow-up period.
- 2. To assess the level of pain during the initial 30 days \pm 7 days post-ablation.

